#### 6.10 Analysis of baseline characteristics

Baseline data including demographics, anamnestic data, vital signs and laboratory values will be summarized by treatment group. Analyses will be repeated in SAF, FAS and PPS.

#### 6.11 Analysis of Efficacy Endpoints

All efficacy endpoints will be assessed for FAS, PPS and SAF.

#### 6.11.1 Analysis of Primary Endpoint

Primary study endpoint:

The hypothesis H0 is tested against the **one-sided** alternative hypothesis H1

```
H0: \mu_{\Delta FBF,Riva, week 20} \leq \mu_{\Delta FBF, ASS, week 20} vs. H1: \mu_{\Delta FBF, Riva, week 20} > \mu_{\Delta FBF, ASS, week 20}
```

by test procedures for continuous data. In case of non-rejection of the normality hypothesis an ANCOVA procedure for repeated measurements will be applied. For repeated measurements per subject an AR(1)-covariance-structure will be specified. Otherwise ANCOVA for repeated measurements will be based on (Blom-transformed) rank data.

Primary endpoint for the extension period:

The hypotheses

```
H0: \mu_{PWV, Riva, week 52} = \mu_{PWV, ASS, week 52} VS. H1: \mu_{PWV, Riva, week 52} \neq \mu_{PWV, ASS, week 52}
```

will be tested by procedure for continuous data.

Age, gender and duration of diabetes might represent confounding factors and could thus be included as covariates in the statistical model. Models incorporating different combinations of covariates are compared with respect to their model fit. The best fitting model according to the QIC (Quasi-Likelihood information) -criterion will be finally chosen for analysis.

Correction procedures for multiple comparisons are not necessary due to the fact that both primary endpoints consist in single comparisons addressing different variables.

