## HO: $\Delta$ FBFRiva $\leq \Delta$ FBFASS H1: $\Delta$ FBFRiva $> \Delta$ FBFASS

- Type I error:  $\alpha$  = 0.05, one-tailed t-test for independent samples
- Power: 1-ß = 0.90
- Estimated dropout rate : 25 %
- Minimum of expected clinical relevant difference between the groups in changes of maximal forearm blood flow ( $\Delta$ FBF) = 1.2 ml/100ml with an estimated standard deviation (SD) of  $\sigma$  = 2.4 ml/100ml [Pistrosch, F. et al. Diabetes Care 27: 484-490, 2004]

Sample size should be N = 188 Patients ( $N_{1/2}$  = 94 patients per arm) for a valid number of 141 patients for per protocol analysis. This sample size may also provide enough power for further analyses.

Additionally, the second primary variable is difference of PWV between treatment groups at EOT Extension (after 52 week of treatment). The sample size calculation is based on the following assumptions:

H0: PWVRiva=PWVASS

H1: PWVRiva≠PWVASS

- Type I error:  $\alpha$  = 0.05, t-test for independent samples

- Power: 1-ß = 0.80
- Estimated dropout rate : 20 %
- Minimum of expected clinical relevant difference between the groups in PWV = 0.7 m/s with an estimated standard deviation (SD) of  $\sigma$  = 1.0 m/s

Sample size should be N=80 patients (40 patients per arm) for a valid number of 66 patients for per protocol analysis.

In summary the necessary sample size would be N=188 patients for the study up to week 20 including 80 patients for the extension up to week 52.

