## 9.2 Statistical methods

Descriptive or summary statistics will be displayed for continuous data and for categorical data. All continuous variables will be summarised using the following statistics: n (non-missing sample size), mean, 95 % confidence interval, standard deviation, median, maximum and minimum. The frequency and percentages (based on the non-missing sample size) of observed levels will be reported for all categorical measures. In general, all data will be listed, sorted by subject and visit number. All summary tables will be annotated with the total population size relevant to that table/treatment, including any missing observations.

Comparisons will be tested at the 2-sided 5% significance level. For the primary study endpoint, a one-sided significance level of 5% will be assumed.

T-tests for independent samples will be used for single comparisons between treatment arms (like the primary study endpoint). Analyses of the continuous variables over time will be performed as paired t-Test, repeated measures analysis of variance or mixed models. All analyses of categorical measures will be performed using Fisher's exact test, McNemar's Test or  $\chi^2$  test. Previous correlation analyses of outcome variables and possible predictors will provide evidence for inclusion in analysis. In this trial, most relevant time points for analyses of longitudinal data for secondary study endpoints are at baseline (V1) and after end of treatment (V6).

Individual listings of treatment-emergent adverse events will be provided. The incidence of treatment-emergent adverse events, respectively, will be summarized using WHO SOC terms. Analysis of adverse events will be based on the safety analysis set.

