#### 4.8 Definition of derived variables

#### 4.8.1 Primary variable

#### ΔFBF:

 $\Delta$ FBF (ml/100ml) will be composed of 5 IR baseline measurements and 8 measurements of post-ischemic blood flow. Repeated measurements for IR baseline per visit will be summarized by arithmetic mean.

Changes in FBF (ml/100ml) will be calculated as IR post-ischemic – IR baseline (mean).

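### AR(1) is the only covariance named for the primary FBF model and the SE type is not stated; with model-based SEs the one-sided 5% test could reject about 5% to 12% of the time under the null

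*SAP*

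**What the plan says.** **Variable.** SAP 4.8.1 says that ΔFBF "will be composed of 5 IR baseline measurements and 8 measurements of post-ischemic blood flow". On the resting part it says: "Repeated measurements for IR baseline per visit will be summarized by arithmetic mean". Change in FBF is then the post-ischaemic value minus that mean. The mock tables in SAP 7.6.1 have rows for Post1 to Post8, each minus baseline.

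**Model.** SAP 6.11.1 tests one mean per arm at week 20: "The hypothesis H0 is tested against the one-sided alternative hypothesis H1". If normality is not rejected, a repeated-measures ANCOVA is used, and "For repeated measurements per subject an AR(1)-covariance-structure will be specified". Otherwise the repeated-measures ANCOVA is run on Blom-transformed ranks. SAP 6.3 adds the baseline value as covariate. No random patient effect, alternative structure or SE type is named. Covariates are chosen by QIC.

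**Level.** Protocol 9.2: "For the primary study endpoint, a one-sided significance level of 5% will be assumed".

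**Sample size.** Protocol 9.1.8 and SAP 2.4 rest on a t-test for independent samples, that is, one value per patient.

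**The concern.** Under AR(1) the correlation between two readings is ρ to the power of their lag, with one variance throughout. By the eighth reading the implied correlation with the first is ρ⁷, which is 0.008 at ρ = 0.5. Readings taken minutes apart in one arm, all reduced by the same resting mean, may instead keep a common component at every lag, from the patient's own level and from error in that mean. If so, AR(1) credits the eight readings with more independent information than they hold. A model-based SE for the pooled treatment effect is then too small, and a one-sided claim for rivaroxaban is easier than the stated 5% allows. The SAP wording permits a programmer to fit exactly that model, so the validity of the primary p-value depends on a software choice that the plan does not make.

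**Working it through.** **1. The plan's own figure.** Inputs from Protocol 9.1.8: one-sided α 0.05, "Power: 1-ß = 0.90", difference 1.2, SD 2.4, 25% dropout.

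- Normal approximation: n = 2 × (1.645 + 1.282)² × (2.4/1.2)² = 68.5, so 69 per arm.
- Noncentral t: 70 per arm (power 0.903; 69 gives 0.899), 140 in total against the plan's 141.
- 141 / 0.75 = 188.

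The plan's figure is reproduced. It contains no within-visit correlation, so every correlation below is an assumption.

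**2. What the subtraction does.** With post-ischaemic readings Pᵢ and resting mean R:

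Cov(Pᵢ − R, Pⱼ − R) = Cov(Pᵢ, Pⱼ) − Cov(Pᵢ, R) − Cov(Pⱼ, R) + Var(R).

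Var(R) enters every pair equally. The two middle terms can offset it, so the net shared part may be larger or smaller than before subtraction.

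**3. Model-based against true variance.** Take eight readings of variance 1, a patient-constant share s, and residual AR(1) correlation φ. The AR(1) model closest in likelihood has ρ = s + (1 − s)φ. Its model-based variance of the pooled effect, up to a factor common to both variances, is (1 + ρ)/(8 − 6ρ). The true variance is w′Sw, where S is the assumed covariance and w holds the generalised least squares weights. Actual one-sided error = 1 − Φ(1.645 × SE_model/SE_true).

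Worked case, s = 0.5 and φ = 0, so ρ = 0.5:

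- Model variance: 1.5/5 = 0.30.
- Weights: 0.2 for the first and last reading, 0.1 for the six between. Sum of squares: 2 × 0.04 + 6 × 0.01 = 0.14.
- True variance: 0.5 + 0.5 × 0.14 = 0.57.
- SE ratio: √(0.30/0.57) = 0.725. Critical value in effect: 1.645 × 0.725 = 1.193. Error: 11.6%.

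**4. The range.**

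| Assumed structure | One-sided error, model-based SE |
|---|---|
| Constant correlation 0.05 / 0.1 / 0.2 / 0.3 | 7.0% / 8.5% / 10.4% / 11.4% |
| Constant correlation 0.42 (maximum; SE 72% of true) | 11.8% |
| Constant correlation 0.5 / 0.8 / 0.9 | 11.6% / 9.0% / 7.3% |
| φ = 0.3, s from 0.2 to 0.7 | 8.0% to 9.1% |
| φ = 0.6, s from 0.2 to 0.7 | 6.2% to 6.9% |
| φ = 0.9, largest over the s tried | 5.2% |
| Only the error of the mean of 5 resting readings is shared; one resting reading's error variance 0.1 / 0.5 / 1.0 times that of a post reading | 5.8% / 8.2% / 9.9% |
| Correlation 0.4, φ = 0, SD falling linearly from 1 to 0.2 | 10.0% |
| s = 0.5, φ = 0.6, SD falling by e^−0.2 per reading (to 0.25 of the first) | 5.3% |
| s = 0.7, φ = 0.6, the same fall | 4.7% |
| s = 0.5, φ = 0.6, SD falling by e^−0.3 per reading (to 0.12 of the first) | 4.4% |
| True AR(1), no shared part | 5.0% |
| Only two repeated measurements (AR(1) equals constant correlation) | 5.0% |

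**5. Simulation.** The runs had 70 per arm, AR(1) by REML and a reading-matched baseline covariate, with 1,500 runs per scenario. Monte Carlo SE at 5% is √(0.05 × 0.95/1500) = 0.6 percentage points.

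- Model-based SE: 11.4% and 12.1% with equal correlation (patient and visit share 0.5 and 0.6); 8.4% with share 0.8; 6.7% to 7.1% with serial correlation plus a shared part; 5.3% with true AR(1).
- Patient-clustered sandwich SE, same AR(1) working structure: 4.1% to 5.9% across all scenarios.
- ANCOVA on one mean per patient: 4.6% to 5.4%.

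**The case against.** The strongest reply is that the inflation depends on choices the SAP does not make.

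- **SE type.** QIC is a criterion for GEE, where AR(1) is a working correlation and robust SEs are usual. With those the test holds its level. This stands: a reader might infer that the planned SE is too small, or that the planned test has a 12% error rate, and the documents support neither. But 6.11.1 describes an ANCOVA with a specified covariance and requires no robust SE, so QIC hints at the answer without settling it.
- **Repeated factor.** The SAP does not say whether it is readings, visits or both. The eight readings are the likely choice from 4.8.1 and 7.6.1, but this is an inference. With one value per visit, as in the maximal-flow variable of Protocol 6.1.1, the eight-reading problem does not arise.
- **Size.** The ceiling needs no serial correlation, yet Protocol 6.2.1 places the cycles seconds apart on one recovery curve. Serial correlation lowers the error.
- **Falling variance.** A reader might infer that any patient-constant part inflates the error, or that unequal variance makes it worse. Neither holds in general: steeply falling variance with strong serial correlation gave 4.4% to 5.3%. Falling variance alone is no cure, since without serial correlation it still gave 10.0%.
- **Pooled effect.** The change table in 7.6.1 has a group comparison for each of Post1 to Post8. With treatment-by-reading terms, balanced data and equal variances, each such contrast has the right SE under AR(1). That is correct, but 6.11.1 states a single hypothesis, which eight separate contrasts do not answer.
- **Baseline covariate.** It can absorb persistent patient variation. The simulation included one, and inflation remained wherever a shared component at week 20 remained.

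**Conclusion.** The concern holds in conditional form. AR(1) is the only covariance named for readings that plausibly share a non-fading component, and the SE type is left open. If the repeated factor is the eight readings, the treatment effect is pooled over them and SEs are model-based, the one-sided 5% test could reject about 5% to 12% of the time under the null. The upper end needs constant correlation of roughly 0.3 to 0.5 with no serial decay. Residual lag-1 correlation of 0.3 to 0.6 gives about 6% to 9%, and adding a steep fall in variance gives about 4% to 5%. With patient-clustered robust SEs the error is about 5%. These figures rest on assumed correlations and on untransformed data; the rank-based fallback was not examined. Neither the presence nor the direction of an error in the eventual analysis is established. What is established is that following the SAP sentence with model-based SEs can give an invalid primary p-value. Severity: should-fix, before the analysis is programmed.

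**What to change.** In SAP 6.11.1, name the repeated factor and replace the AR(1) sentence with one of the following, applied to the rank-based fallback as well:

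- **(a)** One pre-specified FBF value per patient and visit, compared at week 20 by ANCOVA on its baseline value, with no repeated-measures covariance. This matches the one-value-per-patient t-test basis of the sample size. Which FBF value to use is a separate question that the SAP must also settle.
- **(b)** The repeated-measures model with an unstructured within-visit covariance (8 × 9/2 = 36 parameters for eight readings at one visit), or any working structure with sandwich standard errors clustered on patient. State that the reported p-value and confidence interval use these.

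Option (a) is the simpler. The cost is a short SAP edit and a program option, and possibly a slightly wider interval.

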# Pulse wave velocity and arterial stiffness:

	Measurements will be performed using the Mobil-O-Graph device (IEM Inc., Stolberg, Germany). This device allows the non-invasive oscillometric analysis of blood pressure and pulse wave over 24 hours. Based on pulse wave analysis we calculate the aortic augmentation index as marker of arterial stiffness and pulse wave velocity. The Mobil-O-Graph device has been validated against gold standard procedures such as applanation tonometry (SphygmoCor, AtCor Inc.).	
Measurement of	Assessment of platelet activation and mitogenic potential	
results	Platelet activation will be assessed by measuring platelet derived microparticles (PMP) by separating platelet poor plasma from platelet rich plasma. Subsequently, analysis of platelet microparticles and their mitogenic potential will be performed after sample thawing. PMP will be measured after staining with anti-GP1b antibodies by fluorescence-activated cell sorting (FACS). In addition, magnetic beads linked with anti-GP1 b antibodies will be used to extract PMP from platelet poor plasma. Extracted PMP will then be added to human vascular endothelial cells (HUVECS) and migration (Boyden chamber) as well as proliferation (BrdU) of HUVECs will be assessed with and without PMP with samples from patients undergoing platelet inhibition or rivaroxaban treatment. Platelet rich plasma will be used to measure platelet activation by cGMP dependent phosphorylation of vasodilator-stimulated phosphoprotein (VASP) at Ser-157 which will be detected by flow cytometry.	
Statistical methods	Efficacy: The statistical analysis will be done in the intention to treat and per protocol set. The primary parameter will be the maximum FBF at 20 weeks (assessed with venous occlusion plethysmography after forearm ischemia) controlling for baseline FBF and the Pulse Wave Velocity (PWV) at EOT (extended treatment period after 52 weeks) assessed with a sphygmograph (Mobilograph®, IEM) using an analysis of covariance (ANCOVA). Independent t-test will be used to test the parameters between the groups at the time point as well as the change between baseline and 20 weeks of treatment. Additionally, measurements will also be compared to an extended treatment up to 52 weeks (EOT Extension). Safety: Analysis of bleeding events and safety parameters is required.	

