## 6.2 Applied measurement procedures

### 6.2.1 Venous occlusion plethysmography for assessment of forearm blood flow FBF:

Endothelium dependent vasodilation of resistance vessels will be assessed in both arms simultaneously using strain-gauge venous occlusion plethysmography (Gutmann Medizinelektronik, Eurasburg, Germany or Hokanson Pletysmograph EC6). Patient rest for at least 20 min in supine position in a temperature controlled room. At both upper arms a cuff for venous occlusion will be placed. On the forearm, at the side of its maximal circumference an elastic straingauge is used to assess changes of the forearm circumference after release of the upper arm cuff. At start of each assessment of postischemic vasodilation the upper arm cuff will be inflated to 20 Torr above the arterial blood pressure (but at least 200 Torr) for 5 min to induce forearm ischemia. Thereafter the upper arm cuff will be released for free arterial blood inflow into the forearm. Every 10 sec the upper arm cuff inflates automatically to 40 Torr to induce venous congestion for about 10 sec. These sequences will be repeated 10 times. During venous congestion the arterial blood inflow into the forearm causes an increase of its circumference which depends on the amount of blood inflow. The latter one is determined by forearm vascular resistance due to the arteriolar tense.

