#### 6.3 Hypothesis Testing

Unless otherwise specified all hypotheses will be tested at a 5% level of significance against two-sided alternative hypotheses.

Continuous variables will be analyzed by the following test procedures:

First of all the assumption of normally distributed data will be checked with Shapiro-Wilk test by treatment group. If the hypothesis of normally distributed data cannot be rejected for both treatment groups treatments will be compared by an ANCOVA procedure which includes "treatment" as the main factor and "baseline value" as covariate. T-Tests for independent samples will be used to compare groups at baseline.

In the event that the normality assumption is not warranted, data will be log-transformed and normality assumption of the transformed data will be checked by Shapiro-Wilk test. In case of non-rejection of the hypothesis of normally distributed data for both treatment groups, ANCOVA procedure and t-tests as described above will be performed on the basis of log-transformed data.

Point estimates and 95% CI of the difference in (adjusted) mean change from baseline will be provided if data are evaluated on basis of an ANCOVA procedure.

Otherwise Mann-Whitney's-U test on the basis of original data will be applied for comparison of groups at baseline. Mann-Whitney's-U test on the basis of intra-individual differences to baseline will be applied for treatment comparison per visits after baseline. Wilcoxon's signed rank test will be applied to evaluate changes from baseline per treatment group.

Categorical variables with 2 categories will be analyzed using Fisher's exact test (with Yates correction) to compare proportions between treatment groups. Variables with more than 2 categories will be compared by Pearson's Chi-square test. Additionally for each category, the proportions of treatment groups are compared using an (asymptotic) z test. Significant differences in proportions will be flagged, p-values for the z-test will not be shown.

Missing values will not be imputed.

If necessary, modifications of this general procedure will be described in the following sections of chapter 6.

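### The covariates of the primary model are chosen by best QIC on the outcome data, so the adjusted estimate and p-value are not fixed in advance; naming one set per endpoint is a cheap improvement

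*SAP*

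**What the plan says.** SAP 6.11.1 sets out the hypotheses for the two primary endpoints (FBF at week 20, PWV at week 52) and then turns to covariates: "Age, gender and duration of diabetes might represent confounding factors and could thus be included as covariates in the statistical model". It continues: "Models incorporating different combinations of covariates are compared with respect to their model fit". The decision rule is: "The best fitting model according to the QIC (Quasi-Likelihood information) -criterion will be finally chosen for analysis".

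Four other places bear on the same model:

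- SAP 6.3, the general procedure for continuous variables, fixes two terms only: "treatments will be compared by an ANCOVA procedure which includes 'treatment' as the main factor and 'baseline value' as covariate".
- SAP 6.11.1 makes the FBF analysis a repeated-measures ANCOVA: "For repeated measurements per subject an AR(1)-covariance-structure will be specified".
- Protocol 9.2 names a t-test for the primary endpoint and says of predictors: "Previous correlation analyses of outcome variables and possible predictors will provide evidence for inclusion in analysis".
- The protocol synopsis (Statistical methods) gives ANCOVA "controlling for baseline FBF and the Pulse Wave Velocity (PWV) at EOT". Baseline FBF is the only covariate it names; PWV appears there as the second outcome.

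Protocol 5.10 states that the study is open-label. SAP section 1 promises blinded review, but for revisions of the SAP itself.

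**The concern.** By its section 1, the SAP exists to fix the analysis in advance. Here the last step of the primary analysis, the choice of covariates, is taken from fits to the outcome being tested. Nothing requires that step to be done blind to treatment, and nothing names one of the eight models as primary and the others as supportive.

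Two things are at stake. The first is whether the reported standard error and p-value, which take no account of the selection, still have their nominal properties. The second is whether two competent analysts following the SAP would report the same number.

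**Working it through.** **1. The plan's own figure.** Inputs for FBF (protocol 9.1.8, SAP 2.4): difference 1.2, SD 2.4, one-sided α 0.05, power 0.90, dropout 25%.

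- Normal approximation: n per arm = 2(1.645 + 1.282)² × (2.4/1.2)² = 68.5, so 69 per arm, 138 in all; 138/0.75 = 184.
- Exact t-test: 70 per arm, 140 in all; 140/0.75 = 186.7, so 187.
- From the stated evaluable number: 141/0.75 = 188. Exact power at 141 is 0.905.

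The 188 reproduces. It does not depend on the covariates, so a fixed set leaves it unchanged.

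**2. Number of candidate models.** Three optional covariates give 2³ = 8 subsets. With intercept, treatment and baseline always present, the residual degrees of freedom are:

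- FBF, 141 patients: 141 − 3 = 138 with no extra covariate, 141 − 6 = 135 with all three.
- PWV, 66 patients (evaluable number in SAP 2.4): 63 and 60.

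**3. Does any passage fix the set?** SAP 6.3 fixes treatment and baseline only. The synopsis stops at baseline FBF. Protocol 9.2 leaves inclusion to correlations with the outcome. The blinded review in SAP section 1 does not reach this step. So no passage does.

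**4. What the rule leaves open.** The SAP does not say:

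- whether the covariate paragraph, which follows the PWV hypothesis, also governs FBF;
- whether treatment and baseline stay in every model during selection;
- whether selection is repeated in FAS, PPS and SAF, all used for efficacy under SAP 6.11, which could give three different models for one endpoint;
- whether the model is fitted by GEE, the method to which QIC belongs.

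**5. Type I error if the rule is followed.** Simulation under no treatment effect, 10,000 trials per row, nominal 5%, one-sided for FBF and two-sided for PWV. Treatment and baseline are forced in. The subset with the lowest N·log(RSS/N) + 2p (AIC, p = number of parameters) is chosen, as a stand-in for QIC with one outcome per patient. The share of outcome variance explained by the three covariates is an assumption, because the documents give none.

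| Endpoint | Variance explained | Best-fit selection | All three fixed |
|---|---|---|---|
| FBF, 141 | 0% | 5.2% | 4.9% |
| FBF, 141 | 10% | 5.2% | 4.9% |
| FBF, 141 | 30% | 4.8% | 4.8% |
| PWV, 66 | 0% | 5.3% | 5.1% |
| PWV, 66 | 10% | 6.0% | 5.4% |
| PWV, 66 | 30% | 5.4% | 5.2% |

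Monte Carlo standard error: √(0.05 × 0.95/10,000) = 0.2 points. Only the PWV row at 10% stands clearly above nominal, by about 1 point.

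**6. How much the result can move with the model.** A further simulation (3,000 trials per setting) let baseline explain 25% of variance and the three covariates 0–30%, with true effects below plan: 0.3 SD for FBF and 0.5 SD for PWV, against planned values of 1.2/2.4 = 0.5 SD and 0.7/1.0 = 0.7 SD. The eight models disagreed on significance in 6–33% of FBF trials and 10–35% of PWV trials. For PWV at 10% explained variance, the most frequently selected model won in only 28% of trials. Disagreement becomes rarer as the true effect approaches the planned one.

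**The case against.** The strongest reply is that this is a prespecified selection rule. The three candidates, the criterion and the decision are written down, and QIC ranks models on fit, not on the treatment p-value. That stands, and it is why the table shows little inflation. It does not settle the open items in step 4, and it does not make the final model known in advance.

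Three stronger readings are tempting, and the documents do not support them.

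- *QIC cannot be used here.* A reader might infer this because the SAP speaks of ANCOVA. But a repeated-measures model with AR(1) correlation can be fitted by GEE, which yields QIC. The fair criticism is that the fitting method is not stated.
- *The plan's error rate is 6–11%.* Reporting the smallest of the eight p-values would give 5.8–9.8% for FBF and 6.4–11.1% for PWV. That means ignoring the QIC rule, so these figures describe a breach of the SAP and not the plan's own error.
- *Plethysmograph type belongs in the same set.* Protocol 6.2.1 allows two devices ("Gutmann Medizinelektronik, Eurasburg, Germany or Hokanson Pletysmograph EC6"), but PWV is measured with another instrument, and SAP section 4 lists no device variable.

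It can also be said that the protocol calls the trial explorative (9.1.5) and a pilot (2.1). This lowers the stakes. Both documents nevertheless state formal primary hypotheses with α and power, and those need a defined model.

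**Conclusion.** The point holds in a limited form. The primary covariate set depends on the outcome data of an open-label trial, and no other passage of either document fixes it. Followed mechanically, the rule costs 0 to about 1 point of type I error. That figure rests on AIC standing in for QIC, one outcome per patient, normal errors, independent covariates of equal strength, and treatment and baseline in every model. The AR(1) repeated-measures model itself was not simulated.

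The case for change is therefore mainly reproducibility: the headline estimate and p-value should not depend on which of eight models wins. This is a cheap improvement and not a flaw that invalidates the analysis.

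**What to change.** Replace the covariate paragraph of SAP 6.11.1 with a statement along these lines: for FBF at week 20, and separately for PWV at week 52, the primary model contains treatment, the baseline value of that outcome, age, gender and duration of diabetes, whatever their fit or significance. Delete the QIC step, or list other combinations as sensitivity analyses. State the fitting method, and apply the same terms in FAS, PPS and SAF. Align protocol 9.2 by removing the correlation-based inclusion rule and reconciling its t-test with the ANCOVA in the synopsis and SAP. Do this before outcome data are examined by arm.

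A baseline-only model, as in the synopsis, would also remove the selection step. Fixing all three covariates keeps the adjustment that the SAP evidently wants.

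Cost: one SAP paragraph and the matching text in protocol 9.2. No new data are needed, since SAP 4.1 and 4.2 already list the three variables, and the sample size does not change. The statistical price is at most 3 degrees of freedom (138 to 135 for FBF, 63 to 60 for PWV). In the simulation of step 6, fixing all three cost at most 3 points of power when they explained nothing, and otherwise under 1 point.
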